Sorafenib will be given at a dose of 400 mg, orally, twice a day. Possible adverse events related to sorafenib include: cardiovascular: hypertension (9% to 17%); central nervous system: fatigue (37% to 46%), sensory neuropathy ($\leq 13\%$), pain (11%); dermatologic: rash/desquamation (19% to 40%; grade 3: $\leq 1\%$), hand-foot syndrome (21% to 30%; grade 3: 6% to 8%), alopecia (14% to 27%), pruritus (14% to 19%), dry skin (10% to 11%), erythema; endocrine & metabolic: hypoalbuminemia ($\leq 59\%$), hypophosphatemia (35% to 45%; grade 3: 11% to 13%; grade 4: $< 1\%$); gastrointestinal: diarrhea (43% to 55%; grade 3: 2% to 10%; grade 4: $< 1\%$), lipase increased (40% to 41% [usually transient]), amylase increased (30% to 34% [usually transient]), abdominal pain (11% to 31%), weight loss (10% to 30%), anorexia (16% to 29%), nausea (23% to 24%), vomiting (15% to 16%), constipation (14% to 15%); hematologic: lymphopenia (23% to 47%; grades 3/4: $\leq 13\%$), thrombocytopenia (12% to 46%; grades 3/4: 1% to 4%), INR increased ($\leq 42\%$), neutropenia ($\leq 18\%$; grades 3/4: $\leq 5\%$), hemorrhage (15% to 18%; grade 3: 2% to 3%; grade 4: $\leq 2\%$), leukopenia; hepatic: liver dysfunction ($\leq 11\%$; grade 3: 2%; grade 4: 1%); neuromuscular & skeletal: muscle pain, weakness, respiratory: dyspnea ($\leq 14\%$), and cough ($\leq 13\%$).

The early reports of serious adverse events possibly associated with the use of TheraSphere included death, hepatorenal failure, liver abscess, hepatic encephalopathy, hepatic decompensation, radiation hepatitis, radiation pneumonitis, duodenal ulcer, gastrointestinal bleeding and cholecystitis. As clinical experience with TheraSphere increased, the pre-treatment high risk factors associated with these early serious events were identified, leading to improved patient selection criteria and thereby lowering the risk of these events occurring. These risk factors include infiltrative tumor type, bulk disease (tumor volume $> 70\%$ or nodules too numerous to count), AST or ALT $>$ five times the upper limit of normal, bilirubin > 2 mg/dL, tumor volume $> 50\%$ in the presence of an albumin < 3 g/dL and those in whom extra-hepatic shunting to the lungs or gastrointestinal tract cannot be managed through standard angiographic techniques.

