5.1.1 Inclusion criteria

1. Subjects must be able to understand and be willing to sign the written informed consent form. A signed informed consent form must be appropriately obtained prior to the conduct of any trial-specific procedure.
2. Male or female patients ≥ 18 years of age
3. Life expectancy of at least 12 weeks (3 months).
4. Patients with histological or cytologically documented HCC (Documentation of original biopsy for diagnosis is acceptable if tumor tissue is unavailable) or clinical diagnosis by AASLD criteria in cirrhotic subjects is required {Bruix, 2005}. For subjects without cirrhosis histological confirmation is mandatory.
5. Patients must have at least one tumor lesion that meets the following criteria: The lesion can be accurately measured in at least one dimension according to RECIST
6. The target lesion(s) has not been previously treated with local therapy (such as surgery, radiation therapy, hepatic arterial therapy, chemoembolization, radiofrequency ablation, percutaneous ethanol injection or cryoablation).
7. Patients who have received local therapy, such as surgery, radiation therapy, hepatic arterial embolization, chemoembolization, radiofrequency ablation, percutaneous ethanol injection or cryoablation are eligible if the previously treated lesions have progressed or recurred can be identified as target lesions. Local therapy must have been completed at least 4 weeks prior to the baseline scan.
8. Patients who have received Yttrium-90 microspheres are not eligible.
9. Patients who have an ECOG PS ≤ 1
10. Patients who are categorized under BCLC-C stage
11. Cirrhosis grade of Child-Pugh class A. Child-Pugh status should be calculated based on clinical findings and laboratory results during the screening period.
12. The following laboratory parameters:
 - a. Platelet count $\geq 60 \times 10^9/L$
 - b. Hemoglobin ≥ 8.5 g/dL
 - c. Total bilirubin ≤ 2.5 mg/dl
 - d. Alanine transaminase (ALT) and AST ≤ 5 x upper limit of normal
 - e. Serum creatinine ≤ 1.5 x the upper limit of normal
13. Prothrombin time (PT)-international normalized ratio (INR) ≤ 2.3 or PT ≤ 6 seconds above control.
14. All acute toxic effects of any prior treatment have resolved to NCI-CTCAE v4.0 Grade 1 or less at the time of signing the Informed Consent Form (ICF).

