5.1.2 Exclusion criteria

1. Main portal vein thrombosis (PVT)
2. Patients who are eligible for curative treatment (ablation or resection or transplantation)
3. Previous or concurrent cancer other than HCC unless without evidence of disease for 5 or more years prior to entry, except cervical cancer in-situ, treated basal cell carcinoma, or superficial bladder tumor.
4. Tumor replacement >70% of total liver volume based on visual estimation by the investigator OR tumor replacement >50% of total liver volume in the presence of albumin <3 mg/dL
5. Contraindications to angiography and selective visceral arterial catheterization
6. Any known contraindications to sorafenib including allergic reaction, pill-swallowing difficulty, uncontrolled hypertension or history of cardiac disease, significant GI bleed within 30 days, metastatic brain disease, renal failure requiring dialysis
7. Concomitant treatment or within 28 days of one of the following:
 - a. Any other systemic anticancer agent other than agents used for cancer prevention
 - b. Subjects who have used strong CYP3A4 inducers (eg, phenytoin, carbamazepine, phenobarbital, St. John's Wort [*Hypericum perforatum*], dexamethasone at a dose of greater than 16 mg daily, or rifampin [*rifampicin*], and/or rifabutin) within 28 days before treatment.
 - c. UGT 1A1 and UGT 1A9 substrates (e.g., irinotecan)
 - d. P-Gp substrates (e.g., Digoxin)
8. Prior radiation therapy to the liver
9. Prior systemic therapy for the treatment of HCC, including sorafenib
10. Any history of symptomatic pulmonary compromise, such as chronic obstructive pulmonary disease
11. Any prior intervention for, or ongoing compromise of, the Ampulla of Vater or biliary-enteric anastomosis.

12. Clinically evident ascites (trace ascites on imaging is acceptable)
13. Pregnant or breast-feeding patients
14. A positive serum pregnancy test within 14 days prior to treatment in women of childbearing potential
15. Uncontrolled hypertension (systolic pressure >140 mm Hg or diastolic pressure > 90 mm Hg [NCI-CTCAE v4.0] on repeated measurement) despite optimal medical management.
16. Active or clinically significant cardiac disease including:
 - a. Congestive heart failure – New York Heart Association (NYHA) > Class II.
 - b. Active coronary artery disease.
 - c. Cardiac arrhythmias requiring anti-arrhythmic therapy other than beta blockers or digoxin.

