Prior to first TheraSphere treatment a Tc-99m MAA scan will be performed to obtain a preliminary assessment of hepatic infusion and any potential extrahepatic shunting or gastrointestinal flow. Lung Shunt Fraction will be determined as the ratio of total lung counts divided by total hepatic plus lung counts.

If gastrointestinal flow is detected, steps will be undertaken (embolization, change in catheter position) to correct this flow, prior to TheraSphere administration. If gastrointestinal flow cannot be corrected using established angiographic techniques, the patient may not receive TheraSphere treatment.

Only after extrahepatic exposure has been evaluated and the patient deemed to meet eligibility criteria, may TheraSphere be administered.

To be eligible to receive TheraSphere treatment, the potential absorbed dose to the lungs must be < 30 Gy (< 16.5mCi of injected activity) per treatment. Any uncorrected detectable gastrointestinal flow is a contraindication to TheraSphere treatment.

Treatment Planning

The principal investigator with the Authorized User will formulate the initial treatment plan, indicating the number and sequence of planned TheraSphere treatments. The clinician will assure that the patient understands the two-stage screening process that is necessary for this treatment procedure. The physician and patient will discuss and agree on a contingency treatment plan, including the option of no treatment, in the event that the patient is found ineligible to receive TheraSphere after catheter placement. The Treatment Plan may be modified following initial treatment, based on clinical experience and patient response to treatment.

TheraSphere Dose Calculation

The target dose of TheraSphere used is 80 – 150 Gy. Depending on the timing of the product order relative to the TheraSphere production schedule, and the treatment date proposed for the patient, it may be necessary to allow TheraSphere to physically decay to the appropriate targeted activity before injection.

The amount of radioactivity required to deliver the dose to the selected liver target is calculated using the following formula:

$$\text{Activity Required (GBq)} = \frac{[\text{Desired Dose (Gy)}][\text{Mass of Selected Liver Target (kg)}]}{50}$$

In nearly all cases more than 95% of the glass microspheres are delivered. Calculation of the liver dose (Gy) delivered after injection uses the following formula:

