$$\text{Dose (Gy)} = \frac{50 [\text{Injected Activity (GBq)}][1-F][1-R]}{\text{Mass of Selected Liver Target (kg)}}$$

Where F is the fraction of injected activity deposited into the lungs as measured by Tc-99m MAA and R is the calculated residual.

TheraSphere Ordering

The TheraSphere order will be placed by the Authorized User or designated colleague. Upon completion of the pre-treatment screening evaluation, treatment plan and dose calculation, a TheraSphere order form will be sent to TheraSphere Customer Support, either by E-mail to [contact] or by fax to [name]). The deadline for order is the Tuesday **prior** to calibration date to permit inclusion of your order in the weekly dispensing cycle.

TheraSphere is viable for therapeutic use for up to 12 days after the calibration date. TheraSphere will be shipped by MDS Nordion to ensure that TheraSphere is on-site by the proposed treatment date. To meet the desired absorbed dose to the patient's liver, the clinician must schedule the patient's TheraSphere treatment visit to occur within 12 days of the calibration date, and take into consideration the appropriate physical decay of the dose activity.

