7.1 Schedule of procedures

7.1.1 Tabulated overview

CLINICAL AND LABORATORY EVALUATIONS [Table 7]

	Pre-Study [@]	Cycle 1, Day 1	Cycle 2 & Subsequent Cycles Day 1 ^f , #	End of Cycle 3, 5, & every 2 cycles [#]	End of Treatment #	Post Treatment Follow-up
Informed consent	X					
Demographics	X					
Medical History	X		X		X	
Concurrent Medications*	X		X		X	
Physical Exam	X		X		X	
Height	X					
Weight	X	X	X		X	
Vital Signs (Includes SBP/DBP)	X	X	X		X	
Urinalysis w/urine protein	X			X	X	
Performance status	X		X		X	
Hepatitis profile ⁱ	X					
PT/PTT/INR ^a	X		X		X	
CBC with differential, platelets	X		X		X	
Serum chemistry ^b	X		X		X	
Liver function tests ^c	X		X		X	
ECG	X					
β-HCG (women of child-bearing potential)	X					
AFP ^d	X		X		X	
CT/MRI abdomen and pelvis Tumor Assessment ^e	X			X	X	
TheraSphere		Therapy 4 (+/- 1) weeks after starting Sorafenib				
Sorafenib		Daily continuous 400 mg, orally, twice a day				
Adverse events	X ^g		X		X	
Survival						X ^h
Plasma samples ^j	X	X	Cycles 2, 3, day of Y-90		X	

[@] Pre-study evaluations except for imaging studies, Hepatitis profile must be obtained within 7 days prior to first day of treatment. Baseline imaging studies may be obtained up to 28 days prior to first day of treatment. Hepatitis profile must be obtained within 3 months prior to first day of treatment

[#] Evaluations may be obtained within (+/-) 72 hours of starting a new cycle, except for imaging studies which may be obtained within 7 days prior to starting a new cycle.

*All medications, including prescription and over-the-counter, vitamins, supplements and

"herbal" preparations must be disclosed by the patient and recorded. Patients will be instructed to check with study staff before taking any new prescription or over-the-counter medication(s), vitamins, supplements and/or "herbal" preparations

^a Weekly monitoring of INR for patients on warfarin, however, these patients will be switched to enoxaparin if possible.

^b Includes BUN, creatinine, sodium, potassium, carbon dioxide, chloride, phosphorus, magnesium, calcium, protein, glucose.

^c Includes AST (SGOT), ALT (SGPT); total, direct and indirect bilirubin; LDH, alkaline phosphatase, albumin; (GGT will be run for alkaline phosphatase that is ≥ 150 IU/L. GGT will be run with the first elevation of alkaline phosphatase and will not be repeated for future alkaline phosphatase elevations)

^d Alpha-feto protein.

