11.1 Ethical and legal conduct of the study

The procedures set out in this protocol, pertaining to the conduct, evaluation, and documentation of this study, are designed to ensure that the investigator abide by Good Clinical Practice (GCP) guidelines and under the guiding principles detailed in the Declaration of Helsinki. The study will also be carried out in keeping with applicable local law(s) and regulation(s).

Documented approval from appropriate IEC(s)/IRBs will be obtained for all participating centers before start of the study, according to GCP, local laws, regulations and organizations. When necessary, an extension, amendment or renewal of the EC/IRB approval must be obtained and also forwarded to Bayer.

Strict adherence to all specifications laid down in this protocol is required for all aspects of study conduct; the investigator may not modify or alter the procedures described in this protocol.

Modifications to the study protocol will not be implemented by the investigator without discussion and agreement by Bayer. However, the investigator may implement a deviation from, or a change of, the protocol to eliminate an immediate hazard(s) to the trial subjects without prior IEC/IRB/Bayer approval/favorable opinion. As soon as possible, the implemented deviation or change, the reasons for it and if appropriate the proposed protocol amendment should be submitted to the IEC/IRB/head of medical institution. Any deviations from the protocol must be explained and documented by the investigator.

The Principal Investigator is responsible for the conduct of the clinical trial at the site in accordance with Title 21 of the Code of Federal Regulations and/or the Declaration of Helsinki. The Principal Investigator is responsible for personally overseeing the treatment of all study patients. The Principal Investigator must assure that all study site personnel, including sub-investigators and other study staff members, adhere to the study protocol and all FDA/GCP/NCI regulations and guidelines regarding clinical trials both during and after study completion.

The Principal Investigator at each institution or site will be responsible for assuring that all the required data will be collected and properly documented.

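### Exclusion 4 prints the albumin threshold in mg/dL instead of g/dL, so its >50% tumour arm cannot trigger; the activity figure attached to the lung-dose limit in Section 6.3 is also mislabelled

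*Combined protocol and SAP*

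**What the plan says.** Exclusion 4 in Section 5.1.2 has two arms. The first excludes patients whose liver is more than 70% replaced by tumour, judged visually by the investigator. The second excludes "tumor replacement >50% of total liver volume in the presence of albumin <3 mg/dL".

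Section 2.3 lists the pre-treatment factors linked to early serious events after TheraSphere. It includes the same pairing, tumour volume above 50% "in the presence of an albumin < 3 g/dL", and says that recognising these factors changed practice, "leading to improved patient selection criteria and thereby lowering the risk of these events occurring".

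The laboratory list in Section 5.1.1 (item 12) sets limits for platelets, haemoglobin, bilirubin, ALT/AST and creatinine, but none for albumin. Item 11 requires Child-Pugh class A and says that "Child-Pugh status should be calculated based on clinical findings and laboratory results during the screening period". Albumin is measured before study entry as part of the liver panel (Table 7, footnote c: "total, direct and indirect bilirubin; LDH, alkaline phosphatase, albumin").

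On the lung limit, Section 6.3 states that "the potential absorbed dose to the lungs must be < 30 Gy (< 16.5mCi of injected activity) per treatment". Under the dose formula in the same section, "F is the fraction of injected activity deposited into the lungs as measured by Tc-99m MAA".

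**The concern.** Both statements of the albumin rule use the number 3 and the 50% tumour cut-off, and both sit beside a 70% cut-off. Only the unit differs, and the version with the implausible unit is the one staff must apply. A threshold in mg/dL disables one of the two arms of an exclusion meant to keep high-risk patients from Y-90. The early serious events listed in Section 2.3 include death, hepatic decompensation and radiation hepatitis. The trial also monitors treatment-related non-haematological toxicity of grade 3 or higher with a stopping rule (Section 8.1), so who is admitted bears on what that rule observes. Section 11.1 adds that "Strict adherence to all specifications laid down in this protocol is required for all aspects of study conduct"; staff should not have to override printed text to apply the intended criterion.

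The lung sentence has a related fault. It gives a fixed injected activity as the equivalent of a fixed lung dose, although the share of injected activity that reaches the lungs differs between patients.

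**Working it through.** **Albumin**

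Inputs: threshold 3 mg/dL (Section 5.1.2, item 4); threshold 3 g/dL (Section 2.3).

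- Conversion: 3 mg/dL ÷ 1000 = 0.003 g/dL.
- Ratio of the two thresholds: 3 ÷ 0.003 = 1000.
- Applying each rule to some low albumin values, chosen for illustration:

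| Albumin (g/dL) | In mg/dL | Below 3 g/dL? | Below 3 mg/dL? |
|---|---|---|---|
| 1.5 | 1500 | yes | no |
| 2.0 | 2000 | yes | no |
| 2.5 | 2500 | yes | no |
| 2.8 | 2800 | yes | no |

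Every value that the Section 2.3 threshold would catch passes under the printed one. The >70% arm carries no albumin condition and is unaffected.

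**Lung limit**

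Inputs: 30 Gy, 16.5 mCi, the factor 50 (Gy·kg/GBq) and the target dose of 80 to 150 Gy, all from Section 6.3; 1 mCi = 0.037 GBq. The documents give no lung mass, so 1.0 kg is assumed, with a range of 0.8 to 1.2 kg.

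1. Reproduce the plan's figure, using activity = dose × mass ÷ 50. For 1.0 kg of lung: 30 × 1.0 ÷ 50 = 0.600 GBq, and 0.600 ÷ 0.037 = 16.2 mCi, within 2% of the stated 16.5. For 0.8 to 1.2 kg the result is 13.0 to 19.5 mCi.
2. Work in the other direction. 16.5 × 0.037 = 0.6105 GBq.
   - 1.0 kg: 50 × 0.6105 ÷ 1.0 = 30.5 Gy
   - 0.8 kg: 50 × 0.6105 ÷ 0.8 = 38.2 Gy
   - 1.2 kg: 50 × 0.6105 ÷ 1.2 = 25.4 Gy
   - Mass giving exactly 30 Gy: 50 × 0.6105 ÷ 30 = 1.02 kg
3. So 16.5 mCi corresponds to 30 Gy when all of it lies in about 1 kg of lung. It equals injected activity only if F = 1. At F = 10%, injecting 16.5 mCi gives 0.10 × 30.5 ≈ 3 Gy to the lungs.
4. Read as a cap on injected activity, 0.6105 GBq would limit the liver target to 50 × 0.6105 ÷ 80 = 0.38 kg at 80 Gy, or 50 × 0.6105 ÷ 150 = 0.20 kg at 150 Gy. A 1 kg target needs 80 ÷ 50 = 1.6 GBq to 150 ÷ 50 = 3.0 GBq, that is 43 to 81 mCi.
5. Read as activity in the lungs, the permitted injected activity is 16.5 ÷ F: 330 mCi at F = 5%, 165 mCi at F = 10% and 82.5 mCi at F = 20%.

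**The case against.** The strongest reply is that the albumin unit exposes its own error. No real patient could have an albumin of 0.003 g/dL, the correct value is in the same document, and this is a single-institution trial whose principal investigator oversees treatment personally. Staff would probably apply g/dL. That is fair and limits the practical effect, but it relies on the reader to correct a safety criterion.

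A second reply is that other criteria already screen out poor liver reserve: Child-Pugh A, the bilirubin and INR limits, the exclusion of clinically evident ascites and the >70% arm. These narrow the group who could slip through. They do not replace a rule that combines tumour burden with albumin, and the documents give no albumin cut-offs for Child-Pugh A from which the overlap could be worked out.

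Third, Section 2.3 is rationale, and the protocol does not adopt its whole list. It names bilirubin above 2 mg/dL as a risk factor while eligibility allows up to 2.5, and infiltrative tumours are not excluded. That weakens any claim that every factor there must be a criterion. It does not affect this one, which the protocol did adopt with the same numbers.

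Fourth, Section 1.1 reports no grade 4 or 5 reactions in the first 20 patients. This gives no sign of harm, but it does not show that the criterion was applied as intended.

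On the lung sentence, the 30 Gy limit is clear and governs, and the literal activity cap would err towards under-treatment. The exact match to 16.5 mCi does depend on an assumed lung mass. The mislabelling does not: with F varying between patients, no single injected activity can stand for a fixed lung dose.

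**Conclusion.** The point holds. The albumin threshold in exclusion 4 is 1000 times lower than the one in Section 2.3, and as printed the >50% arm cannot exclude anyone. This follows from the two texts and a unit conversion, with no assumption beyond taking Section 2.3 as the intended value. It should be corrected because it is a decision threshold in operative eligibility text. The likely practical effect is modest, for the reasons granted above, and the number of patients affected cannot be computed.

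The lung label is a secondary wording error. 16.5 mCi is activity deposited in the lungs, consistent with 30 Gy for a lung mass of about 1 kg (assumed). The 30 Gy limit itself is sound. Neither point touches the PFS endpoint, the sample size, the stopping boundaries or their operating characteristics.

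**What to change.** - **Section 5.1.2, item 4:** change the albumin unit from mg/dL to g/dL, to match Section 2.3.
- **Section 6.3:** describe the 16.5 mCi as activity deposited in the lungs, defined as injected activity × lung shunt fraction F, and state the lung mass used (about 1 kg reproduces 30 Gy). Leaving the residual R out of this product is acceptable, because it errs on the safe side. Keep the 30 Gy limit unchanged.

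The cost is two wording corrections in one amendment. Albumin and the lung shunt fraction are already measured before Y-90 treatment, so no new data, patients or statistical work are needed.

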For those patients without the pre-treatment high risk factors noted above, TheraSphere is very well tolerated, with treatment in the US commonly administered in an outpatient setting. Hospitalization for treatment effects associated with TheraSphere administration is rare.

3. Study objectives

The objective of this study is to evaluate the safety of continuous sorafenib 400 mg twice daily followed, after 3-5 weeks, by Yttrium-90 treatment in patients with child-Pugh A, BCLC-stage C HCC.

Primary objective:

- Median progression-free survival (PFS)

Secondary objectives:

- Overall survival (OS)
- Time to radiographic progression (TTRP)
- To evaluate the safety of the combination of sorafenib and Yttrium-90; Adverse events (NCI-CTAE v 4.0)
-

[figure not shown]
Other objectives:

Predictive Biomarkers of response to therapy and survival: will assess pre-treatment plasma level of IGF-1 as above, and assess its predictive ability of TTP and OS

4. Study design

This is a single-arm phase II clinical trial to evaluate the safety of continuous sorafenib at 400 mg twice daily followed, after 4 (+/- 1 week) weeks from starting sorafenib, by Yttrium-90 treatment concomitant with sorafenib, in patients with child-Pugh A, BCLC-stage C HCC. Of note, the time between starting sorafenib and Yttrium-90 administration will be 4 weeks regardless whether the patient underwent dose reductions or interruptions. Patients will continue taking the maximum tolerating dose of sorafenib, with no interruption during and after the Yttrium-90 procedures. This is a single-institution study that will be conducted at MDACC, Department of GI Medical Oncology and Department of Interventional Radiology. No sorafenib interruptions around the procedure will be applied, and only one Y-90 treatment only will be performed.

Study schema:

5. Study population

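### Exclusion 4 gives the albumin limit in mg/dL instead of g/dL, so read literally its >50% tumor-replacement limb excludes no one (wrong as written, minor)

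*Combined protocol and SAP*

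**What the plan says.** Section 5.1.2, exclusion 4, removes a patient on either of two grounds. The first is tumor occupying more than 70% of the liver on the investigator's visual estimate, with no albumin condition. The second is "tumor replacement >50% of total liver volume in the presence of albumin <3 mg/dL".

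Section 2.3 describes how early serious events with TheraSphere led to a list of pre-treatment risk factors and to better patient selection. One entry pairs tumor volume above 50% with low albumin: "in the presence of an albumin < 3 g/dL".

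Three other places bear on how exclusion 4 is applied:

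- Section 11.1: "Strict adherence to all specifications laid down in this protocol is required for all aspects of study conduct".
- Section 6.3: "Only after extrahepatic exposure has been evaluated and the patient deemed to meet eligibility criteria, may TheraSphere be administered".
- Section 7.1.1, footnote c, includes albumin in the liver function tests done pre-study: "total, direct and indirect bilirubin; LDH, alkaline phosphatase, albumin".

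**The concern.** The two statements share the 50% tumor threshold and the number 3 and differ only in the unit. Exclusion 4 is the operative text, because it decides who may enter; Section 2.3 is background. If the operative text has the wrong unit, a safety exclusion that the protocol meant to impose has no force as written.

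At stake is a specific kind of patient: large intrahepatic tumor burden, short of 70%, with low albumin. Section 2.3 says that selection on its list of factors as a whole lowered the risk of early serious events, which included hepatic decompensation and radiation hepatitis. It does not credit this one factor separately.

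**Working it through.** **Inputs**

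- Printed limit: albumin <3 mg/dL with tumor replacement >50% (Section 5.1.2, exclusion 4).
- Background limit: albumin <3 g/dL with tumor volume >50% (Section 2.3).
- Conversion: 1 g = 1000 mg.

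**Step 1: do the two limits agree?** 3 mg/dL ÷ 1000 = 0.003 g/dL. Ratio of the two limits: 3 ÷ 0.003 = 1000. They do not agree.

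**Step 2: whom does each version exclude?** Take a patient with replacement above 50% and up to 70%, so that only the albumin limb can act. The albumin values are illustrative, not trial data.

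| Albumin (g/dL) | Same in mg/dL | Excluded as printed (<3 mg/dL) | Excluded if limit is <3 g/dL |
|---|---|---|---|
| 1.0 | 1000 | No | Yes |
| 2.0 | 2000 | No | Yes |
| 2.5 | 2500 | No | Yes |
| 2.9 | 2900 | No | Yes |
| 3.0 | 3000 | No | No |
| 3.5 | 3500 | No | No |

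Even the lowest value in the table is 1000 ÷ 3 ≈ 333 times the printed limit. The printed limb therefore excludes nobody over this range. With the unit corrected, the cut falls between 2.9 and 3.0 g/dL, as Section 2.3 intends.

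**Step 3: does any other text supply the limit?**

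- The synopsis repeats the main inclusion criteria but not the exclusions.
- The laboratory limits in Section 5.1.1, item 12, do not include albumin.
- Section 6.3 adds a laboratory review, a lung-dose limit and a bar on uncorrected gastrointestinal flow before TheraSphere is given. None of these names an albumin value.

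Of the text available, only the background in Section 2.3 gives the limit in the right unit.

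**The case against.** The strongest reply is that this is a typing slip which no one would apply literally. The intended value is in the same document, a limit of 3 mg/dL makes no clinical sense, and a screening investigator would read g/dL. The adherence clause in Section 11.1 is general wording and hardly obliges staff to use an impossible unit. There is also a separate clinical and laboratory evaluation before TheraSphere, and Child-Pugh class A is required. If that class is scored in the usual way, with albumin as a component, the lowest albumin values are already screened out. The US package insert (Appendix 1a) is not in the text available and may state the limit.

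Most of this stands, and it is why the point is minor. It does not make the criterion correct. An eligibility threshold should be usable as printed, and excluding a patient at 60% replacement and 2.9 g/dL currently means departing from the text.

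Two stronger readings are tempting, and the documents support neither.

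- A reader might infer that unsuitable patients were enrolled or harmed. Section 1.1 reports no grade 4 or 5 reactions in the first 20 patients. The results are not split by baseline albumin or tumor burden, so they neither show harm nor rule out misclassification.
- A reader might infer a matching error for bilirubin, because item 12c admits "Total bilirubin ≤ 2.5 mg/dl" while Section 2.3 lists "upper limit of normal, bilirubin > 2 mg/dL" among the risk factors and adds: "For those patients without the pre-treatment high risk factors noted above, TheraSphere is very well tolerated". That does not follow. Section 2.3 lists risk factors, not contraindications. Other entries, such as infiltrative tumors and uncountable nodules, are not exclusions either. Section 2.3 also cites a cohort in which patients with raised bilirubin were treated, and reports its conclusion that treatment was safe in compromised liver function. The bilirubin limit is a design judgment; the albumin unit is a mistake.

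**Conclusion.** Wrong as written, minor. The albumin limit in exclusion 4 is 1000 times too low, and read literally one of the criterion's two limbs has no effect. This conclusion rests on unit conversion and on one safe assumption: no patient has an albumin below 0.003 g/dL.

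The number of patients affected cannot be derived from the documents and is probably small. It depends on how staff read the unit and on how many Child-Pugh A patients combine replacement above 50% and up to 70% with albumin below 3 g/dL. The protocol gives neither the Child-Pugh scoring table nor the distribution of these values, so no count is offered. With 20 patients enrolled and a maximum of 40, at most 40 − 20 = 20 remain to be screened in under this criterion. That is remaining enrollment, not an estimate of those exposed.

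The point does not touch the sample size, the toxicity boundaries, the futility rule or the comparison with a median of 4.1 months in Section 8.1.

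**What to change.** In Section 5.1.2, exclusion 4, change the unit of the albumin limit from mg/dL to g/dL, so that the second limb reads as tumor replacement above 50% with albumin below 3 g/dL. Nothing else needs to change: not the >70% limb, the other eligibility criteria, or the monitoring tables.

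The cost is one unit in one line. Albumin is already measured pre-study, so no test or visit is added. If staff have been reading g/dL all along, the correction brings the text into line with practice and does not alter the population.
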